1.0 Objectives

Objectives and Aims

The objective of this project is to develop and pilot test a text messaging intervention to increase human papillomavirus (HPV) vaccination in young adult men who self-identify as gay, bisexual, or queer (which for the sake of brevity, will be referred to as MSM throughout this application, although some men will be sexually inexperienced).

Specific Aim 1: Develop, iteratively refine, and pre-test messages using a 5-step formative research procedure. To achieve this aim we will use a well-established formative approach for designing targeted health interventions. The procedure consists of 5 steps: 1) conduct online focus groups, an online survey, and in-depth interviews to inform message content, 2) draft initial messages based on focus group findings and pilot data, 3) refine message content and assess acceptability using content advisory teams, 4) conduct internal alpha testing to ensure software functionality, and 5) beta test the protocol. Intended users of the program (i.e., MSM aged 18-26 years old from the Chicago metro area) will be recruited to assist with this process.

Specific Aim 2: Test the feasibility, acceptability, and preliminary efficacy of the txt2protect (t2p) text messaging intervention in a pilot randomized controlled trial (RCT). To achieve this aim, 460 unvaccinated MSM (ages 18-26) who live in the Chicago metro area will be randomly assigned to the treatment (t2p) or control condition. The treatment condition will receive a culturally appropriate text messaging-based HPV vaccination intervention based on the IMB model, whereas the control condition will receive a text messaging-based sexual health intervention that includes basic facts about HPV vaccination readily accessible online. Primary outcome measures include intervention feasibility (recruitment and retention in the trial), acceptability (satisfaction with the intervention), and preliminary efficacy as determined by initiation (receipt of the first dose) and completion of the 3-dose HPV vaccine series at the end of the 9-month trial. Vaccination status will be verified by participants' medical records and the Illinois Immunization Registry.

Hypotheses

Specific Aim 2: Participants in the t2p condition (vs. control) will report greater acceptability of the intervention and will be significantly more likely to initiate and complete the 3-dose HPV vaccine series by the end of the trial.

2.0 Background

Significance and Innovation

HPV is a common STI that can cause cancer (anal, penile, oropharyngeal cancer) and genital warts in men.¹ Due to their sexual practices (e.g., receptive anal intercourse), **MSM are at particularly high risk for HPV infection and are disproportionately affected by HPV-related cancers.** Over a 1-year study, for example, oncogenic HPV types 16 and/or 18 were detected in 37% of MSM aged 16-30 years.² Rates of anal cancer are over 17 times higher among MSM relative to heterosexual men,³ and the burden of anal cancer is exceptionally high among HIV-positive MSM.⁴ In addition to cancer, HPV causes genital warts, which are costly to treat and negatively impact quality of life.⁵ **A safe and effective vaccine is available to prevent HPV infection, yet HPV vaccination rates in the U.S. have been disappointingly low, particularly among males.** The quadrivalent HPV vaccine (for types 6, 11, 16, 18) and more recently, the 9-valent HPV vaccine (plus types 31, 33, 45, 52, 58) are extremely effective in preventing

PROTOCOL TITLE: txt2protect

HPV infection.^{1,6} The HPV vaccine is given as a 3-dose series, with the 2nd and 3rd doses administered 1-2 and 6 months after the 1st dose, respectively. The Advisory Committee on Immunization Practices (ACIP) recommends *routine* HPV vaccination in 11- and 12-year-old girls and boys, and catch-up vaccination among 13-26 year-old females and 13-21 year-old males not previously vaccinated, although males aged 22-26 may also be vaccinated.¹ Although HPV vaccine is most effective in sexually naïve youth, given their high-risk status, ACIP recommends HPV vaccine for all MSM up to age 26 regardless of whether they have been sexually active, as it is unlikely they have been exposed to all HPV types covered by the vaccine.^{1,6} Nationally, HPV vaccine uptake in males lags far behind females: About 60% of adolescent females have received at least one dose of the vaccine compared to only 41.7% of males.⁷ A similar disparity holds for completion of the 3-dose series (39.7% of females vs. 21.6% of males).⁷ **Although HPV vaccine is recommended for all MSM though age 26 years, relatively few have been vaccinated.** Recent studies with national samples of gay and bisexual men aged 18-26 found that only 13-21% had initiated the series.^{8,9} Our pilot work suggests that many MSM are simply unaware of the vaccine or perceive other important barriers to getting vaccinated. **To remedy this gap, the goal of the proposed research is to develop and pilot test a text messaging intervention to increase HPV vaccination in young MSM.** This contribution is significant because it will identify new strategies for promoting HPV vaccination among a high-risk population. Beyond these more immediate outcomes, the ultimate goal of this research is to reduce morbidity, mortality, and disparities associated with HPV-related cancers among MSM. This work will also shed light on factors that affect use of other health services for young MSM that, like vaccination, typically involve interaction with the health care system (e.g., HIV testing, mental health screening and treatment).

Although MSM are disproportionately affected by HPV-related cancers, **this group has been neglected in previous HPV vaccination research.** Research has centered largely on parents and young adult women.¹⁰⁻¹⁸ While such work has identified important factors that promote and/or discourage HPV vaccination, it falls short of recognizing factors that may be unique to young MSM. **Existing research suggests relatively high acceptance of HPV vaccine among MSM;¹⁹⁻²⁸ nevertheless many of these studies have significant limitations:** 1) they were conducted prior to ACIP's 2011 recommendation for *routine* HPV vaccination among boys and men and thus were hypothetical in nature, 2) involved MSM older than age 26 years, and 3) lacked a strong theoretical framework.²⁹ To our knowledge, only two studies (one by our team) have been conducted with young adult gay and bisexual men since HPV vaccination became routine for males in 2011.^{8,9} **As the HPV vaccination intervention field is still in its relative infancy, no known HPV vaccination interventions have been designed specifically for MSM.** In addition to its focus on young MSM, the proposed research is innovative in several ways: 1) Our intervention will *target young adults directly* rather than indirectly through their parents. 2) We will build on and further strengthen an existing evidence-based intervention for vaccination ("reminder-recall") by including messages that *address barriers to HPV vaccine uptake with special emphasis on barriers unique to MSM.* 3) Because our pilot data identified provider recommendation as the strongest predictor of HPV vaccination,⁸ several *messages will come directly from a physician specializing in sexual minority health.* To facilitate this objective we have partnered with one of the largest LGBT health care centers in Chicago, Howard Brown Health Center (HBHC). 4) We will encourage participants to receive HPV vaccine in primary care clinics as well as at pharmacies. Pharmacies have been identified as a *promising alternative setting for increasing HPV vaccination rates*, particularly for

PROTOCOL TITLE: txt2protect

promoting completion of the 3-dose series due to their convenient locations and longer hours of operation.^{30, 31} 5) We will be recruiting participants directly from the community and thus will be able to *extend the reach of the intervention to those individuals who might not normally see a physician.*^{32, 33} Together, these elements reflect a novel approach to promoting HPV vaccination among young MSM.

Preliminary Data

HPV vaccination among young MSM. To inform the proposed project, Drs. [name], [name], and [name] conducted a pilot study to identify barriers and facilitators to HPV vaccine uptake among young MSM.⁸ We recruited a national sample of 336 MSM aged 18-26 to complete an online survey. 21% had received ≥ 1 dose of HPV vaccine. Provider recommendation was the strongest predictor of uptake such that MSM with a recommendation were over 40 times more likely to have been vaccinated. We also observed disparities in uptake, with lower rates among 21-26 year-olds (vs. 18-20), Latinos (vs. Whites), and HIV-negative (vs. HIV-positive) men. Primary barriers to uptake included lack of information about HPV and the vaccine, lack of provider recommendation, and not having disclosed their sexual identify to their provider.

Reducing barriers to HPV vaccination. In previous work (R03CA138069), [name] identified primary barriers to HPV vaccine uptake among young adult women aged 18-26³⁴ and demonstrated that tailoring intervention materials to women's perceived barriers increased their intentions to receive HPV vaccine.³⁵ Intervention materials addressed common barriers to uptake including lack of information about HPV and the vaccine, concerns about side effects and vaccine safety, low perceived need due to not being sexually active or in a committed relationship, disliking shots, and vaccine cost. In the proposed RCT, we will use a *targeted approach*^{36, 37} such that treatment messages will be specifically designed for MSM (e.g., provide tips to address common and unique barriers to HPV vaccine uptake among young MSM).

Guy2Guy (G2G): A text messaging intervention for young MSM. To design our messages we will follow the 5-step procedure used to develop Guy2Guy³⁸ (G2G; R01MH096660, [name] & Ybarra, Multiple PIs), a text messaging-based HIV prevention intervention for adolescent gay, bisexual and queer men. MSM were randomly assigned to the treatment (a culturally appropriate HIV prevention and healthy sexuality intervention that was informed by the target population and guided by the IMB model³⁹) or control arm (that provided basic HIV prevention facts plus healthy lifestyle information). Participants received 5-10 text messages daily for 5 weeks. In addition to being highly feasible and acceptable,^{38, 40} short-term outcome analyses found that the rate of condomless sex acts over the course of the intervention was 61% lower in treatment vs. control (although long term effects were more modest). Of particular relevance to the proposed study, participants in the treatment group were over twice as likely to get tested for HIV relative to control.

Rationale

Reminder-recall and text messaging interventions. Reminder-recall interventions are a well-established evidence-based approach to increasing vaccination that are endorsed by the US Task Force on Community Preventive Services.^{41, 42} The goal of these interventions is to both educate and notify individuals that they are due (or overdue) for a vaccine. Historically, reminder-recall interventions used letters, postcards, or telephone calls, but have recently transitioned to electronic formats such as text messages and email. Text messages (or short-message service, SMS) serve as particularly effective reminders in that, relative to a letter or postcard, they are more likely to grab attention, reach the intended recipient, and because they can be stored on

PROTOCOL TITLE: txt2protect

a cellular phone, can be easily accessed almost any time.⁴² Beyond providing basic education and a cue to action, text messages can be tailored to address barriers to vaccine uptake. Although research is still accumulating, text messaging-based interventions appear to be a promising, cost-effective strategy for promoting health behaviors.⁴³⁻⁴⁵ Such interventions may be particularly effective for young adults, as nearly all young adults in the U.S. own a cell phone (mainly a smartphone) and 97% use text messaging.⁴⁶ We chose to create a text messaging intervention rather than a smartphone application because text messages can be sent proactively and are routinely used by the target age group.

Theoretical framework. The theoretical framework guiding the proposed project is the Information, Motivation, and Behavioral Skills (IMB) model.³⁹ This model, originally developed for HIV prevention, proposes that individuals will engage in a given health behavior when they are adequately informed, motivated to act, and have the appropriate behavioral skills and self-efficacy do to so. Text messages can provide basic information (e.g., about HPV and the vaccine; convenient locations to get vaccinated such as a pharmacy) and serve as a reminder (e.g., to schedule an appointment, to receive the 2nd or 3rd dose). They can also boost motivation (e.g., by promoting favorable attitudes and norms; by addressing barriers like safety concerns) and improve necessary skills (e.g., talking with one's doctor about the vaccine, verifying health insurance coverage).

[figure not shown]

Figure 1. Guiding Theoretical Framework

3.0 Inclusion and Exclusion Criteria

Specific Aim 1

Participants for this project will be self-identified gay, bisexual, and queer males between the ages of 18-26 years who provide informed consent to participate. (Please note that the upper age limit will be reduced to age 25 for the beta test and RCT so participants will continue to remain eligible for HPV vaccination throughout the length of the study.) Participants will be recruited online through ads placed on websites and dating apps such as Facebook, Twitter, Grindr, Craigslist, and Jack'd, a strategy that has been extremely successful by the current team across multiple NIH-funded projects and in a number of metropolitan areas across the U.S. including Chicago.^{40, 47-49}

ResearchMatch.org will also be utilized as a recruitment tool. ResearchMatch.org is a national electronic, web-based recruitment tool that was created through the Clinical & Translational Science Awards Consortium in 2009 and is maintained at Vanderbilt University as an IRB-approved data repository (see IRB #090207). Participants may also be recruited from existing participant registries (e.g., Institute for Sexual and Gender Minority Health and Wellbeing [ISGMH]; Third Coast Center for AIDS Research [CFAR]).

Interested participants will be directed to a screening survey where eligibility will be assessed. The **inclusion criteria** will closely match that of the intended users of the eventually designed program and be consistent with the latest CDC guidelines for HPV vaccination. Participants must:

- 1) be male (sex at birth and gender identity)

PROTOCOL TITLE: txt2protect

- 2) be 18-26 (*Upper age limit will be age 25 for the beta and RCT) years old
- 3) self-identify as gay, bisexual, or queer; ever had sex with a man; or be physically attracted to men
- 4) be English speaking
- 5) live in the Chicago metro area
- 6) be the exclusive owner of a cell phone
- 7) have used text messaging for at least 6 months
- 8) plan to have the same cell phone number for the next 9 months
- 9) be enrolled in an unlimited text messaging plan

The screener will also assess HPV vaccination status, which will be confirmed by consulting the Illinois Immunization Registry before enrollment. Vaccinated and unvaccinated participants will take part in Step 1, but Steps 3 and 5 will be limited to unvaccinated participants. Participants will be selected using a purposive sampling strategy to ensure a sample that is diverse in age, race, ethnicity, and sexual identity. Individuals meeting inclusion criteria will be contacted by telephone to complete the enrollment process (e.g., confirm eligibility, describe the study).

Specific Aim 2

Inclusion criteria will be identical to Aim 1 except that enrollment will be limited to individuals who have not been previously vaccinated for HPV. HPV vaccination status will be assessed twice – once in the screener and again in the baseline survey – before participants are randomized and enrolled into the study. Participants' self-reported vaccination status in the screener and baseline survey will be confirmed by consulting the Illinois Immunization Registry before enrollment.

Special Populations

We will not be recruiting any special populations (e.g., adults unable to consent, individuals who are not yet adults, pregnant women, or prisoners) for this project.

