Step 3: Refine messages and assess acceptability. We will use content advisory teams (CATs) to further refine the messages. CAT1 and CAT2 will focus on treatment condition messages and CAT3 will focus on control condition messages. CAT members will receive an email link to the list of initial messages hosted on a secure web-based application called REDCap and will be asked to provide feedback on their overall tone, clarity, and appeal, and to identify their favorite and least favorite messages (See Appendix 2 for draft survey). Several days later, CAT members will take part in a 2-day online FG (similar to Step 1) to discuss the messages as a group and provide suggestions for improvement. Feedback from CAT1 will be used to further refine the messages. This process will then be repeated with another team (CAT2). CAT3 will complete this process for control condition messages. See Appendix 3 for a sample FG guide.

Step 4: Test software functionality. We will conduct alpha testing with the study team to ensure that the text messaging software is functioning correctly. In addition, we will verify the enrollment process and randomization procedure, assess message delivery and display, and correct any programming bugs.

PROTOCOL TITLE: txt2protect

Step 5: Beta-test the protocol. To identify opportunities for improving program usability and to ensure functionality we will beta test the protocol. Twenty participants will be recruited for the beta test. Participants will complete a baseline survey and then receive 5-10 messages daily (similar to the number sent in G2G) for 3 weeks (similar to Phase 1 of the pilot RCT described below). At the end of week 1 and 2, participants will receive a brief check-in survey to provide open-ended feedback on the program. After the final week of messages (week 3), participants will complete a final check-in survey plus additional items to assess intervention acceptability and immediate outcomes of interest (e.g., HPV/HPV vaccine knowledge, IMB constructs, intentions to get vaccinated). See Appendix 4 for draft surveys associated with the Beta-test.

Research Design for Aim 2

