22.0 Recruitment Methods

Participants will be recruited online through ads placed on websites and dating apps such as Facebook, Twitter, Grindr, Craigslist, and Jack'd. ResearchMatch.org will also be utilized as a recruitment tool. ResearchMatch.org is a national electronic, web-based recruitment tool that was created through the Clinical & Translational Science Awards Consortium in 2009 and is maintained at Vanderbilt University as an IRB-approved data repository (see IRB #090207). Participants may also be recruited from existing participant registries (e.g., Institute for Sexual and Gender Minority Health and Wellbeing [ISGMH]; Third Coast Center for AIDS Research [CFAR]). Participants may also be recruited from Howard Brown Health clinics through passive recruitment. Howard Brown staff will post flyers with txt2protect study information, including a link to the online eligibility screener, in clinic waiting areas and other spaces deemed appropriate.

Interested candidates will be directed to complete the screening survey, which will assess eligibility criteria. All eligible candidates will then be directed to complete an online informed consent form. Eligible candidates will be informed that they will be contacted by the Study Manager with information about next steps for taking part in the study.

Interested candidates recruited from paid dating app ad campaigns (e.g. Grindr and Jack'd) who screen as ineligible will be directed to an optional, online survey on smoking and e-cigarettes. The study team has added this supplemental survey because of the high cost of dating app ad campaigns and the anticipated large number of participants who will screen as ineligible. This will allow us to make the most of the large reach of the dating app ad campaigns and collect data that can help inform future research studies on smoking and e-cigarettes, and cancer risk.

Please see supporting documents for sample recruitment ads and the smoking and e-cigarette survey.

PROTOCOL TITLE: txt2protect

Participant Payments

Aim 1

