23.0 Local Number of Subjects

We plan to enroll **950 participants total**.

Aim 1 participants will be recruited to assist with the development of the intervention messages:

Step 1: Four online focus groups with 20 participants per group = **80**

Online survey with 250-300 participants = **300**

In-depth interviews with 25-30 participants = **30**

Step 3: Three content advisory teams with 20 participants per team = **60**

Step 5: Beta test will include 20 participants total = **20**

Aim 2, participants will be recruited to pilot test the text messaging-based intervention:

PROTOCOL TITLE: txt2protect

Pilot RCT: We will recruit 230 participants per arm (treatment vs. control) = 460

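### The RCT eligibility rule does not bar men who reviewed draft treatment messages or beta-tested the programme in Aim 1, so already exposed men could be randomised to control

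*Combined protocol and SAP*

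**What the plan says.** Section 3.0 (Specific Aim 2) defines the RCT population by reference to Aim 1: "Inclusion criteria will be identical to Aim 1 except that enrollment will be limited to individuals who have not been previously vaccinated for HPV". Earlier in the same section one further difference is given: "the upper age limit will be reduced to age 25 for the beta test and RCT". Prior participation in Aim 1 is not mentioned.

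On the Aim 1 men:

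- Section 3.0 says that "Steps 3 and 5 will be limited to unvaccinated participants".
- Section 9.0 (Step 3) says that "CAT1 and CAT2 will focus on treatment condition messages and CAT3 will focus on control condition messages". Members rate a list of initial messages and then discuss it in a two-day online group.
- Section 9.0 (Step 5) has beta testers receive daily messages for three weeks, on the pattern of RCT Phase 1. It does not say which arm's content they get.
- Section 23.0 gives the sizes: "Three content advisory teams with 20 participants per team" and "Beta test will include 20 participants total".

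Recruitment channels are shared. Section 22.0 lists the same websites and apps for the whole project and adds: "Participants may also be recruited from existing participant registries". Section 7.0 places Aim 1 in the first 10 months and opens RCT recruitment in month 11. The check before randomisation in Section 28.0 looks only for HPV vaccine doses.

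**The concern.** A content-team member or beta tester who is still unvaccinated, still in the Chicago area and no older than 25 meets every written RCT criterion. He can be reached by the same advertisements soon after finishing Aim 1. If randomised to control, he may already have seen active content.

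Three things are then at stake:

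- **Efficacy.** Initiation and completion are compared by chi-square on an intent-to-treat basis (Section 11.0). Prior exposure among controls could raise their uptake and narrow the difference.
- **Blinding.** Section 9.0 (Step 2) wants control content that keeps controls unaware of their arm. A man who helped edit treatment messages could recognise that he is not receiving them.
- **Acceptability.** This is a primary outcome (Section 8.0) that is expected to differ by arm (Section 1.0). Men who helped shape the messages are not neutral raters of them.

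**Working it through.** **Inputs from the documents.** Initiation is assumed to be 18–21% on treatment and 6–8% on control, with two-sided alpha 0.05, 192 per arm analysed and 230 per arm enrolled (Section 11.0). Allocation is 1:1 (Section 9.0). The team and beta-test sizes are in Section 23.0.

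**Step 1: the plan's own figure.** Section 11.0 claims more than 80% power in all scenarios. Two calculations at 192 per arm:

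| Scenario | Pooled normal approximation | Exact, Pearson chi-square |
|---|---|---|
| 18% vs 8% | 83.3% | 84.2% |
| 18% vs 6% | 95.4% | 96.3% |
| 21% vs 8% | 95.4% | 96.0% |
| 21% vs 6% | 99.2% | 99.4% |

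The claim reproduces.

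**Step 2: the exposed pool.** Two teams × 20 = 40 men see draft treatment messages. Adding the 20 beta testers gives 60, and 60/460 = 13.0%. The figure of 60 assumes that the beta test used treatment content. It is a ceiling: Step 3 admits men up to 26, and some will have aged out or been vaccinated.

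**Step 3: dilution model.** Let m exposed men enrol, half to each arm. The exposed share of controls is f = (m/2)/230. Let h be the fraction of the treatment effect that an exposed control carries with him. The control rate becomes

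p_C′ = p_C + f × h × (p_T − p_C).

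The treatment-arm rate is left unchanged. Both m and h are assumptions, because the documents give neither.

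For m = 20 and h = 1: f = 10/230 = 0.0435, and p_C′ = 0.08 + 0.0435 × 0.10 = 0.0843.

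**Step 4: exact power at 192 per arm, 18% vs 8%.**

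| Exposed men enrolled (m) | h | Control rate | Power |
|---|---|---|---|
| 0 | – | 8.00% | 84.2% |
| 15 | 1 | 8.33% | 81.2% |
| 20 | 1 | 8.43% | 80.1% |
| 40 | 0.5 | 8.43% | 80.1% |
| 30 | 1 | 8.65% | 77.9% |
| 60 | 0.5 | 8.65% | 77.9% |
| 40 (advisory teams only) | 1 | 8.87% | 75.6% |
| 60 | 1 | 9.30% | 70.7% |

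At h = 1, power drops below 80% at 21 exposed men by the exact calculation and at 17 by the approximation. With all 60, the difference shrinks from 10.0 to 8.7 percentage points.

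**Step 5: the other scenarios, all 60 at h = 1.** Exact power is 87.7% (18% vs 6%), 87.7% (21% vs 8%) and 96.1% (21% vs 6%).

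**Step 6: after the planned attrition.** 230 × 0.80 = 184 per arm. For 18% vs 8%, exact power is 82.9% with no exposed men and 79.8% with 15 at h = 1.

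**The case against.** The strongest reply is that separate samples were plainly intended. Section 23.0 adds 80 + 300 + 30 + 60 + 20 + 460 = 950 participants, Section 7.0 describes Aim 1 and Aim 2 participants separately, and Section 28.0 uses a different consent form for each step. The screener and consent forms, where a question on prior participation might sit, are not in the text available. Nothing says that Aim 1 men will be invited back. This stands as evidence of intent. A head count is still not an eligibility rule, and the rule that is written lets these men in.

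Exposure can also be overstated. A reader might infer that the advisory teams read the finished treatment programme. The documents support only a review of drafts that were later refined, without scheduled texts, Phase 2 boosters or tailoring to doses received. For the beta test, receipt of treatment content is an inference.

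A reader might also infer bias towards zero through both arms: exposed controls take up the vaccine, and exposed treatment men are known non-responders. The documents do not support this. If exposed men are non-responders, exposed controls need not initiate at the treatment rate, so the two arguments pull against each other. With RCT recruitment opening straight after Aim 1, late beta testers would also have had little time to be vaccinated. A second, longer exposure on treatment could raise uptake. The direction of the effect in that arm is uncertain.

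Finally, this is a pilot of feasibility, acceptability and preliminary efficacy, so a modest loss of power matters less than in a confirmatory trial. That limits the weight of the point but does not remove it.

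**Conclusion.** The gap is real: as written, the criteria admit men with prior exposure to draft treatment messages or to the beta test, and no later check screens them out. The consequence is conditional and probably small. The 80% power claim is at risk only in the 18% vs 8% scenario. That takes roughly 17 to 21 exposed men enrolled at full treatment-level uptake (depending on the power formula), or about 40 at half that effect.

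The 71% figure should not be read as expected power. It combines re-enrolment of all 60, treatment content in the beta test, full treatment-level uptake in exposed controls and the least favourable planning scenario. Nor do the documents show that anyone re-enrolled or that the trial's result is biased. The possible effects on blinding and acceptability ratings cannot be quantified from the documents. This is a cheap improvement, not a flaw that undermines the design.

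**What to change.** Add to the Specific Aim 2 criteria in Section 3.0: *Men who took part in Aim 1 Step 3 (content advisory teams) or Step 5 (beta test) are not eligible for the RCT.* Extend the pre-randomisation check in Section 28.0 to match screener phone number and e-mail against the Aim 1 enrolment list.

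Some RCT participants were enrolled before June 2018 (Section 9.0, Assessments), and a new criterion cannot reach anyone already randomised. For them, flag prior Step 3 or Step 5 participation, report the number by arm, and repeat the initiation, completion and acceptability analyses without them. The flag is fixed before randomisation, so leaving these men out keeps the comparison randomised. Set it before the identifier key is destroyed at the end of the study (Section 11.0).

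The cost is one sentence, one list match and at most 60 + 20 = 80 potential recruits. The match will miss a man who has changed both number and e-mail. Step 1 participants need not be excluded: that step comes before the messages are drafted, so they saw none, and excluding them would cost further recruits.
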